CHAIRLESS CHAIR EXOSKELETON

WORK-PHYSIOLOGICAL-BIOMECHANICAL ANALYSIS OF THE LOWER EXTREMITIES

Head of study (UKT)	[name] & [name]
Director	[name]. [name]
Other researchers (UKT)	[name] (Medicine, Doctoral Student) [name] (Medicine Technique, Bachelor Student)
Contact persons	[name] Institut für Arbeitsmedizin, Sozialmedizin und Versorgungsforschung [name] ☎ [name] ☎ [name] ✉ [contact]
	[name] Institut für Arbeitsmedizin, Sozialmedizin und Versorgungsforschung [name] ☎ [name] ☎ [name] ✉ [contact]

I Abstract

Standing work is associated with increased risks of venous and musculoskeletal disorders; particularly low back pain is commonly reported in prolonged standing work. In manufacturing work, work-stations often do not allow standing aids due to insufficient functional and spatial conditions. In 2014, the car manufacturer Audi introduced the lower leg exoskeleton developed by Noonee to their employees working in the factories. This exoskeleton, the 'Chairless Chair', has the advantage that standing work can be performed while technically sitting on this device. The exoskeleton offers the potential for reduced awkward body postures, but it is unclear which biomechanical loads are influenced and how. This study will evaluate the 'Chairless Chair' in a laboratory setting, by testing its effectiveness in terms of biomechanical parameters, including postural balance, back and neck curvature, and muscular activity of selective muscles. For this purpose, different work settings will be compared, consisting of a mixture of different working heights and different positions (wearing or not wearing the exoskeleton) while performing simulated assembly tasks. The study population will consist of 42 healthy men in the age of 18-40 years old, who will perform 7 different experimental conditions.

II Keywords

Exoskeleton, manual materials handling, musculoskeletal disorders, postural balance, standing work

Table of Content

Table of Content	iii
1 Abbreviations	4
2 Background	4
3 Objectives	5
4 Timetable	5
5 Study Design and Study Population	5
5.1 Study Design	5
5.2 Study Population	7
5.3 In- and Exclusion Criteria	7
5.4 Recruitment	7
5.5 Sample Size	9
6 Study Procedure	9
6.1 Experimental Procedure	9
6.2 Experimental Tasks	10
7 Data Collection	10
7.1 Anthropometry	11
7.2 Posturography	11
7.3 Muscular Stress and Strain	12
7.4 Reference Measurements	12
7.5 Work Performance	13
7.6 Subjective Assessment	14
7.7 Participant Evaluation	15
8 Statistical Analysis	15
9 Risk for the Participant	15
10 Data Protection	16
11 Study Finance	16
12 References	17

1 Abbreviations

ARV	Average Rectified Value
COG	Center Of Gravity
COM	Center Of Mass
COP	Center Of Pressure
EMG	ElectroMyoGraphy
FSA	Force Sensing Array
IED	Inter-Electrode Distance
L3	Lumbar vertebra 3
MdPF	Median Power Frequency
MnPF	Mean Power Frequency
PPI	Pressure Peak Index
RMS	Root Mean Square
RPD	Rating of Perceived Discomfort
% RVC	Percentage of Reference Voluntary Contraction
SD	Standard Deviation
T3	Thoracic vertebra 3
UKT	[Universitäts Klinikum Tübingen]

2 Background

Standing work is associated with an increased risk of venous disorders (Sudol-Szopinska et al. 2011; Ziegler et al. 2003) and musculoskeletal disorders (Werner et al. 2010). Particularly low back pain is a commonly reported disorder in prolonged standing work (Andersen et al. 2007; Gregory and Callaghan 2008). The development of lower limb discomfort is mainly the result of stationary standing, and to a lesser extent of dynamic standing (Balasubramanian et al. 2009). Some studies suggested using aids during standing work to relieve the load of the back muscles and reduce symptoms; however, not every workplace allows the use of standing aids because functional and spatial conditions are insufficient.

One solution to reduce the exposure of employees to associated risks for developing work-related musculoskeletal disorders is to use exoskeletons. Using such devices in dynamic environments has the advantage over, e.g., robotics because it does not need any programming or teaching of robots. Moreover, exoskeletons are worn on the body and do not have to overcome spatial issues. In a recent review, 26 different exoskeletons have been described of which only two were designed to support the lower body during heavy work (de Looze et al. 2015). For low-intensity work, like assembly work in the automobile industry, no study has focused on using exoskeletons to relieve employees while performing the work standing.

Since 2014, Audi has several passive exoskeletons to use in their production lines and factories in Southern Germany, where employees perform different types of assembly work while standing (Feigl 2015; Karius 2015; Stirnemann 2015). The passive exoskeleton, the 'Chairless Chair', provides support for the lower extremities. The system is developed by the Swiss company Noonee (Saameli 2014). The 'Chairless Chair' offers the potential for a reduction of awkward body postures, even in restricted spatial conditions at standing workplaces. It is unclear which physiological and

biomechanical loads are influenced by the 'Chairless Chair' exoskeleton and how. Furthermore, it is not clear whether participants of all body heights will experience the same beneficial effects, if any, when wearing the system.

3 Objectives

This research proposal aims to provide a sophisticated study design in which participants simulate assembly work related to that performed in the Audi factories. With measurements of several physiological and biomechanical parameters, work-physiological-biomechanical analyses will be performed to investigate the influence of wearing the exoskeleton during assembly tasks. The participants included will be grouped according to their body height, enabling us to investigate whether body height influences the effectiveness of wearing the exoskeleton.

4 Timetable

The project consists of four phases (Table 1). First, the study design and measurements need to be prepared, which will take approximately three months. Participants will be recruited during three months and the measurements will take up to three months. The data analysis, evaluation, writing and publication will be spread over five months. The four phases will be performed with some overlap with a total length of the study of about ten months.

Table 1. The timetable for the proposed study that will be completed early 2018.

5 Study Design and Study Population

5.1 Study Design

The laboratory study will include several experimental conditions, being a combination of supported seating or unsupported standing by the exoskeleton, and three different working heights. These seven combinations will be offered to the subjects in a balanced, randomized cross-over design (Latin Square Williams Design; Williams 1949). In each of these seven conditions, three manual materials handling tasks will be simulated in a fixed order but in three different frontal working distances. Because of the three working distances, we will include a multiple of the 14 orders resulting from the Williams Design, striving for a population of 42 subjects.

5.1.1 Independent variables (within-subject factors)

At first, experimental conditions are designed by a combination of working position and working height. We will investigate three different working positions [P]: (1) unsupported standing [US], (2) supported high seating [HS], and (3) supported low seating [LS]. We will investigate three working heights [WH]: high [H], medium [M], and low [L]. The combination of these two independent variables is displayed in Figure 1A. The randomized design for assigning conditions to subjects will be based on an orthogonal Latin Square Design (Figure 1B). A third independent variable considered is working distance, i.e. the distance of the task set-up from the front of the subject: (1) optimal, (2) far, (3) very far; the order of these three working distances will also be varied by assigning them balanced to the subjects. For the order of the three working distances, the outcome of a special type of Latin Square Design, the Williams Design suggests three different orders (for the complete experimental design, see Attachment 8).

A	WH _H	WH _M	WH _L	B	1	2	3	4	5	6	7	8	9	10	11	12	13	14
P_{SS}	V	V	X	1	A	B	C	D	E	F	G	D	E	F	G	A	B	C
P_{HS}	V	V	V	2	G	A	B	C	D	E	F	E	F	G	A	B	C	D
P_{LS}	X	V	V	3	B	C	D	E	F	G	A	C	D	E	F	G	A	B
				4	F	G	A	B	C	D	E	F	G	A	B	C	D	E
				5	C	D	E	F	G	A	B	B	C	D	E	F	G	A
				6	E	F	G	A	B	C	D	G	A	B	C	D	E	F
				7	D	E	F	G	A	B	C	A	B	C	D	E	F	G

A $P_{SS}WH_H$
B $P_{SS}WH_M$
C $P_{HS}WH_H$
D $P_{HS}WH_M$
E $P_{LS}WH_L$
F $P_{LS}WH_M$
G $P_{LS}WH_L$

Figure 1. A. Incomplete Block Design (Williams Design) based on position (P) and working height (WH), resulting in 7 different experimental conditions; B. Latin Square Design for 14 subject, which will be preferably elongated to a replicate of 14 subjects.

We consider three fixed working positions for each subject, standing, high seating and low seating on the Chairless Chair. According to the anatomy of the individual, the optimal working height for each working position can be calculated (Equation 1; in accordance with DIN EN ISO 14738:2009-07). Optimal working heights in Figure 1 correspond to (A) $P_{SS} \times WH_H$, (D) $P_{HS} \times WH_M$, and (G) $P_{LS} \times WH_L$, and are based on an optimal elbow angle of 105° with the upper arm vertical alongside the upper body. The non-optimal working heights deviate -10% and +10% from the optimal working height. In a similar way, the optimal working distance (WD) with respect to the subject (in accordance with DIN EN ISO 14738:2009-07) is calculated (Equation 2) and the non-optimal working distances deviate +15% and +30% from the optimal working distance.

$$WH_{optimal} = length_{elbow-floor} - (\sin(\alpha) \cdot length_{elbow-grasping\ hand}) \quad \text{Eq. 1}$$

$$WD_{optimal} = \cos(\alpha) \cdot length_{elbow-grasping\ hand} \quad \text{Eq. 2}$$

with α the angle (°) with the horizontal position of the lower arm, which is always 15°.

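### Working distance is defined from the front of the subject but calculated from the elbow; a set-up placed as defined moves all three levels outward by the elbow-to-front depth

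*Combined protocol and SAP*

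**What the plan says.** Section 5.1.1 introduces working distance as the third within-subject factor, with three levels (optimal, far, very far), and explains it as "the distance of the task set-up from the front of the subject".

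Later in the same section the working heights are derived from an "optimal elbow angle of 105° with the upper arm vertical alongside the upper body". The section then turns to "the optimal working distance (WD) with respect to the subject", which it says is obtained in a similar way. Equation 2 multiplies the elbow-to-grasping-hand length by the cosine of α, "with α the angle (°) with the horizontal position of the lower arm, which is always 15" degrees. For the other two levels, "the non-optimal working distances deviate +15% and +30% from the optimal working distance".

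In section 8, Table 3 lists working distance as a within-subject factor for the mixed model.

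**The concern.** The definition and the equation start from different points on the body. Equation 2 gives a distance from the elbow joint to the hand. With the upper arm hanging beside the trunk, the elbow will normally lie some way behind the front of the body. Laying off the Equation 2 value from the front therefore adds that depth to the reach.

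Two things are at stake. First, the level labelled optimal would already require reaching forward, so it would not reproduce the arm posture from which the optimal set-up is derived. Second, the far and very far levels would be smaller relative increases over the placed optimum than the plan states. The outcomes include trunk and neck angles (section 7.2) and activity of the shoulder and lower-back muscles (section 7.3), which can be expected to respond to reach. What optimal means, and how large the steps are, therefore matters for interpreting this factor.

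**Working it through.** **Inputs from section 5.1.1:** α = 15°, elbow angle 105°, upper arm vertical, steps of +15% and +30%.

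**Assumed, because the documents give no lengths:** elbow-to-grip length L = 36 cm (range 32 to 40 cm), and elbow-to-front depth d = 5, 10 or 15 cm. With d = 0 there is no shift.

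**Step 1: what Equation 2 measures.** With the upper arm vertical and the forearm 15° below horizontal, the elbow angle is 90° + 15° = 105°, as the plan states. The horizontal distance from elbow to hand is then cos(15°) × L = 0.966 L. This is exactly Equation 2, so its origin is the elbow. Equation 1 is the vertical counterpart, and it does link the elbow to its stated reference, the floor, through the elbow-floor length. Equation 2 has no corresponding term linking the elbow to the front of the body.

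**Step 2: intended reach from the elbow at L = 36 cm.**
- Optimal: 0.966 × 36 = 34.8 cm
- Far: 1.15 × 34.8 = 40.0 cm
- Very far: 1.30 × 34.8 = 45.2 cm

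**Step 3: reach if the same values are laid off from the front.** Reach = k × 0.966 L + d, with k = 1, 1.15 or 1.30. The excess of the placed optimum over the intended one is d / (0.966 L). Relative to the placed optimum, the steps become 0.15 × 34.8 / (34.8 + d) and 0.30 × 34.8 / (34.8 + d).

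| d (cm) | Reach from elbow at the three levels (cm) | Excess over intended optimum | Steps relative to placed optimum |
|---|---|---|---|
| 0 | 34.8, 40.0, 45.2 | 0%, +15%, +30% | +15%, +30% |
| 5 | 39.8, 45.0, 50.2 | +14%, +29%, +44% | +13%, +26% |
| 10 | 44.8, 50.0, 55.2 | +29%, +44%, +59% | +12%, +23% |
| 15 | 49.8, 55.0, 60.2 | +43%, +58%, +73% | +10%, +21% |

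**Step 4: sensitivity to L.** From L = 40 cm down to L = 32 cm, the excess at the optimal level is +13% to +16% for d = 5 cm, +26% to +32% for d = 10 cm and +39% to +49% for d = 15 cm.

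**Step 5: where the placed optimum meets the intended levels.** It equals the intended far reach when d = 0.15 × 0.966 L = 0.145 L (5.2 cm at L = 36 cm). It equals the intended very far reach when d = 0.30 × 0.966 L = 0.290 L (10.4 cm at L = 36 cm).

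**The case against.** The strongest reply is that the phrase about the front of the subject is a gloss introducing the factor, not a placement procedure. It may only indicate direction, since section 5.1 calls the distances frontal. The operational text is the pair of equations. Both use the same forearm length and angle, and together they fix the hand relative to the elbow. Staff working from them with a vertical upper arm would put the grasp point where intended. In addition, the cited ergonomic standard, Attachment 1 (body-part lengths) and Attachment 8 (full design) are not in the available text and may name a landmark.

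This makes literal placement uncertain, and that part stands. It does not remove the mismatch. The only body landmark that section 5.1.1 names for working distance is the front, and the phrase accompanying Equation 2 names none. If an attachment names the elbow, section 5.1.1 still has to agree with it.

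A reader might also infer more than the documents support:

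- *That the optimal level lands at the very far reach.* This needs a depth of about 0.29 of the elbow-to-grip length. The documents give neither figure.
- *That the mismatch turns every cell into a forward reach.* Seven conditions at three distances make 21 cells, and 14 of these lie beyond optimal distance by design. Only the seven optimal-distance cells would change in kind.
- *That individual scaling is lost.* The reach would be 0.966 L + d, so each man's L still enters. Scaling is diluted, because a given d is a larger share of a shorter forearm (10 cm is +32% at L = 32 cm and +26% at L = 40 cm).
- *That the distance comparison fails.* The three levels keep their order within each subject, and the balance of the design does not depend on the reference point.

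**Conclusion.** The point holds as an inconsistency of reference point within section 5.1.1, with a consequence that depends on how the set-up is placed. If it is placed from the front of the body as defined, any depth above zero moves all three levels outward, the optimal level misses the 105° posture, and the steps fall below +15% and +30% of the placed optimum. With an assumed L of 36 cm and d between 5 and 15 cm, the optimal level sits 14% to 43% beyond the intended reach. If staff place it from the elbow, there is no shift.

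What is affected is the meaning of optimal and the size of the distance steps. Comparisons between distances remain possible, but the labels would need qualifying. The correction is worth making before data collection, because the reach actually worked at cannot be restored in the analysis.

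**What to change.** Use one reference point in section 5.1.1. Either of these would do:

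- Define working distance as the horizontal distance from the elbow joint, with the upper arm vertical, to the grasp point. Equation 2 and the percentage steps then stand as written.
- Keep the front of the subject, name the landmark, and subtract each man's measured elbow-to-front depth. Apply +15% and +30% to the elbow-based reach first and subtract afterwards, so that the levels are 0.966 L − d, 1.111 L − d and 1.256 L − d from the front.

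With either option, check the elbow angle at the optimal set-up in each of the three working positions before recording starts, and make Attachments 1 and 8 agree where they touch on this.

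The first option costs a change of wording. The second adds one measurement to the body-part lengths already taken at the first visit (section 7.1).

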5.5 Sample Size

The planned study serves as a pilot study for a future larger research project and is intended to provide, among other things, the basis for a concrete calculation of the number of cases for follow-up projects. For this reason, and considering that we will include 7 experimental conditions with 3 working distances, we think that 21 individuals is the minimum for evaluating the exoskeleton, but we strive for 42 to have a double balanced randomization controlled cross-over design (double Williams Design). The total study population will be divided, based on body height, in three subgroups (Figure 2). The groups are based on (1) $< 25^{\text{th}}$ percentile, (2) 25^{th} to 75^{th} percentile, and (3) $> 75^{\text{th}}$ percentile of the average body height of 18-40 German males. As a result, the subgroup analyses may statistically be somewhat weaker than the overall statistical assessment of 42 participants.

We are mainly interested in recruiting men that fall in between the 25^{th} and 75^{th} percentile of the average German body height distribution, corresponding to Group 2 (Figure 2). The percentiles can be calculated using the formula: $X = \mu + Z \cdot \sigma$, in which μ is the population's mean, Z the z-value belonging to the desired percentile, and σ the population's standard deviation.

6 Study Procedure

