6.1 Experimental Procedure

Before the experiment starts, participants will visit the lab for familiarization with the 'Chairless Chair' and familiarization with the three manual materials handling tasks. They will perform the simulated assembly tasks for about 30 to 45 minutes, of which 15 to 30 minutes while wearing the exoskeleton (3.8 kg) in the different positions. During this first visit, the subjects will also complete the form with general information (Attachment 1), the form with in-/exclusion criteria (Attachment 2) and will be explained in a standardized way about how to report and judge subjective feelings of discomfort (Attachment 3). After familiarization, participants will visit the laboratory a second time during which they will perform the seven experimental conditions (exoskeleton [3], working height [3]) in a preset balanced randomized order (using a Williams Design). Before starting with the true experiment, participants will first be equipped with the measurement devices. After the preparations, participants will perform each experimental condition for ~ 20 min followed by 3-min rest breaks. During the rest break the participant will first walk around and then sit down with wearing the exoskeleton.

After finishing the experimental conditions, subjects will perform 11 trials on the force plate. Two trials will be performed while the subject is wearing the exoskeleton and is standing (1) with only his feet on the force platform while the feet of the 'Chairless Chair' are off the force platform. The trials will be recorded while in low seating and in high seating when wearing the exoskeleton and performing one work cycle in optimal height. These trials should provide insight into the body weight distribution over the own feet and the exoskeleton. Nine other trials will be performed to provide insight into the center of pressure's behavior when performing tasks in different lateral workspaces. The nine trials will include three different positions (unsupported standing, supported high seating, supported low seating) and three different frontal-lateral workspaces (narrow in a range of 120° ,

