6.2 Experimental Tasks

The simulated assembly tasks shall represent the existing assembly tasks at the automotive factories of Audi, including screwing, clip fitting, and cable mounting. The three tasks are presented to the subject on each side of a triangle (2.7 kg; Figure 3). One full work cycle consists of assembling the three subtasks and disassembling the three subtasks: (1) assembling 4 screws with an electrical screw driver, (2) fitting two rows of five clips, (3) mounting three cables to one coupling piece, (4) disassembling 4 screws with an electrical screw driver in reverse, (5) loosen the clips, and (6) loosen the cables to remove the coupling piece. We expressed the task, i.e. the work cycle, in codes of the predetermined motion-time system MTM-1 (Maynard et al. 1948). This system is often used in industry to assess the work pace, which also applies to Audi factories. Using detailed tables of the MTM-1 system, we are able to calculate the MTM-100, the pace corresponding to the work pace that a regular worker should be able to reach. Although Audi strives to work at pace MTM-114 at its factories, we strive for pace MTM-100, which is equal to ~ 80 s per work cycle (for an extensive determination of the MTM-pace, see Attachment 9). A metronome including both visual and auditory feedback will be provided to set this work pace for the simulated assembly tasks, indicating how much time the participant has left in a work cycle (the visual feedback is in accordance with Audi factories, in which employees are shown how much time is left to finish the work cycle in the green, orange or red zone).

During the balance measurements after the experiment performed at the force platform, a n auditory metronome will be set for determining the pace at which subjects should move a 2-kg weight from the one side to the other.

Figure 3. Three manual materials handling tasks. One work cycle consists of assembling the screws, clips, and cables and also disassembling them.

7 Data Collection

Objective data collection includes that of posturography, muscle strain, and work performance; subjective data collection includes feelings of discomfort and an evaluation questionnaire about working with the exoskeleton. All measurement devices are CE certified and data will be collected by researchers familiar with the measurements devices, data extraction, and pseudonymization.

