7.3 Muscular Stress and Strain

During standing work, evaluation of the exoskeleton also includes assessing the level and development of muscle activity in selected muscles. Furthermore, it might also be interesting to investigate whether wearing or not wearing the exoskeleton is associated with any manifestations of muscle fatigue. Activity of selective muscles at the legs, back, and shoulders will be recorded. In the lower leg, the Gastrocnemius Medialis is involved in knee bending. In the upper leg, the Vastus Lateralis contributes to standing by supporting the knee and hip. At the lower back, the Erector Spinae Lumbalis helps holding up the spine. At the shoulder region, the Trapezius Descendens is one of the prone muscles during manual materials handling and is responsible for scapular movements and supports arm movements.

Activity of the muscles will be tracked continuously during the experiment using surface electromyography (EMG). This method uses recording electrodes (42×24 mm, Kendall™ H93SG ECG Electrodes, Covidien, Zaltbommel, the Netherlands) that are attached to the skin's surface overlaying the muscle of interest with an inter electrode distance (IED) of 25 mm. The differential signal (bipolar derivation) of two electrodes placed over one muscle belly, recorded by an amplifier (PS12, THUMEDI® GmbH & Co. KG, Thum-Jahnaback, Germany), gives a firm estimation of that muscle's electrical activity in microvolts (µV). This electrical activity pattern enables us to estimate the magnitude of the muscle activity (amplitude) and the overall firing frequency of the muscle (power frequency). The amplitude can be calculated by the overall root-mean-square (RMS) of the power spectrum of the EMG signal. The median power frequency (MPF) can be calculated from the power spectral density of the EMG signal by calculating the median.

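### Three orders of the three working distances do not form a Williams design (six are needed), so the carry-over balance claimed for distance in sections 5.1.1 and 5.5 is not there

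*Combined protocol and SAP*

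**What the plan says.** Section 5.1 nests distance within condition: the tasks are "simulated in a fixed order but in three different frontal working distances", and because of the three distances "we will include a multiple of the 14 orders resulting from the Williams Design", with a target of 42.

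Section 5.1.1 adds that "the order of these three working distances will also be varied by assigning them balanced to the subjects" and that "the Williams Design suggests three different orders". It refers to Attachment 8 for the complete design. Section 5.5 describes the 42-man plan as a double Williams design, which I read as covering both conditions and distances, and says "we think that 21 individuals is the minimum for evaluating the exoskeleton".

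On timing, section 6.1 says that "participants will perform each experimental condition for ~ 20 min followed by 3-min rest breaks". No pause between distances inside a condition is mentioned.

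Section 8 specifies a linear mixed model with posture, working height, working distance and, if numbers allow, body-height group, plus a random intercept for subject. It names no period or carry-over term for distance.

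**The concern.** A Williams design is chosen so that every level is preceded equally often by every other level; the title of the paper cited for it says that it is balanced for estimating residual effects. The plan meets this for the seven conditions but not, on its own description, for the three distances. In a position-balanced set of three orders, each distance is only ever preceded by one particular other distance.

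If working at one distance changes EMG, posture or performance at the next, part of a reported distance effect belongs to the preceding distance. The analysis in section 8 would not separate the two, and the three-order layout makes it expensive to do so afterwards. This is fixed once men have been allocated.

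**Working it through.** **Inputs.** 7 conditions in 14 orders (Figure 1B); 3 distances, here O (optimal), F (far) and V (very far), in 3 orders (5.1.1); target 42 (5.1). Assumptions: each man keeps one distance order in all seven conditions, there is one value per distance within each condition, carry-over is additive, and within-man errors are independent with SD 1.

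**1. The plan's own figure.** 14 condition orders × 3 distance orders = 42. This reproduces the target.

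**2. Conditions.** Counting neighbours in Figure 1B, all 7 × 6 = 42 ordered pairs occur exactly twice in the 14 orders. The first seven orders contain only 21 of the 42, so the doubling is needed for an odd number of levels.

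**3. Distances.** Three levels have 3! = 6 orders, hence 20 sets of three. Two sets are position-balanced: OFV, FVO, VOF and its mirror VFO, OVF, FOV. None of the 20 is carry-over balanced. The first set contains only the pairs OF, FV and VO, twice each. Only the full set of six is balanced for both, and 2t = 2 × 3 = 6.

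**4. Bias without a carry-over term.** Let c_O, c_F, c_V be the carry-over left by each distance. In a set of three, each distance has a predecessor in two of its three positions.

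| Orders | V − O absorbs | F − O absorbs |
|---|---|---|
| OFV, FVO, VOF | 2/3 (c_F − c_V) | 2/3 (c_O − c_V) |
| VFO, OVF, FOV | 2/3 (c_O − c_F) | 2/3 (c_V − c_F) |
| All six | 1/3 (c_O − c_V) | 1/3 (c_O − c_F) |

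Equal carry-overs give zero bias throughout. For an illustrative graded carry-over of 0, 0.1, 0.2, the bias in V − O is 2/3 × (−0.1) = −0.067 with either set of three, and 1/3 × (−0.2) = −0.067 with six. For F − O it is −0.133, +0.067 and −0.033.

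**5. Precision.** Variance of V − O from least squares with subject, condition, condition position, distance period and distance:

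- Unadjusted: 2/(42 × 7) = 0.0068; standard error √0.0068 = 0.082.
- Adjusted for carry-over, three orders: 0.0340, a ratio of 5.0.
- Adjusted for carry-over, six orders: 0.0085, a ratio of 1.25.

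Detectable difference at 80% power, 2.80 × √variance: 0.23, 0.52 and 0.26 within-man SDs. If a quarter of the within-man variance is man-by-distance (assumption): 0.37, 0.78 and 0.41.

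**6. When adjustment pays.** With six orders, adjusting lowers mean squared error in V − O only if (1/3 × difference)² exceeds 0.0085 − 0.0068 = 0.0017, so if c_O and c_V differ by more than 3 × √0.0017 ≈ 0.12 within-man SDs.

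**7. Conditions again.** Over the full 42-man layout, the bias in every contrast among the seven conditions is zero, with three or six distance orders, and whether or not carry-over also crosses the 3-minute break.

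**8. Fit of six orders.** 42/6 = 7 men per order, so the target stands. Full crossing would need 14 × 6 = 84. At the stated minimum, 21/6 = 3.5 and 21/14 = 1.5, so neither factor balances exactly.

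**The case against.** *Attachment 8 may hold six orders.* It may. The 14 × 3 = 42 arithmetic favours three, but the attachment was not supplied. If it lists six, the fault is one sentence, and section 8 still lacks the terms.

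*Nothing documented points to distance-specific carry-over.* This largely stands. A reader might infer from section 7.3, which asks whether wearing the exoskeleton is "associated with any manifestations of muscle fatigue", and from the fatigue listed in section 9, that the plan expects such carry-over. It does not. Section 7.3 is about wearing the device, and section 9 lists possible side effects over the whole session. Fatigue that builds up over time is a period effect, and three cyclic orders already balance distance over position. If the 20 minutes split equally (assumption), each distance lasts 6.7 minutes. At the stated pace, "which is equal to ~ 80 s per work cycle", that is 5 cycles, so a brief transition effect would be diluted.

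*The alarming figures need special circumstances.* Also fair. With three orders and d the relevant carry-over difference, a 5% test of V − O with no true distance effect would reject in 13% at d = 0.10 and 37% at d = 0.20 within-man SDs. That requires carry-over that differs by distance while distance itself has no effect. If carry-over were a fraction f of a roughly linear distance effect, V − O would only be attenuated by f/3, about 3% at f = 10%. The five-fold variance is not a cost of the plan as written either, since it arises only under an adjustment that the plan does not make.

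*Distance is peripheral.* The objectives in section 3 are exoskeleton wearing and body height, in a self-described pilot. Section 8 also averages values over each condition, so separate distance values are not clearly defined. This lowers the weight of the point but does not make the Williams claim true.

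**Conclusion.** Three orders of three distances are not a Williams design, and the balance claimed for distance does not hold, subject to Attachment 8. That rests on counting alone.

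The consequence is limited to distance contrasts and depends on a carry-over difference of unknown size; if it is zero, there is no bias. With three orders, the bias in V − O reaches one standard error when 2/3 × d = 0.082, that is d ≈ 0.12 within-man SDs, under the error assumptions in the working.

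Three stronger readings are not supported. The exoskeleton and height comparisons among the seven conditions are not biased at 42 men, given additive carry-over and one distance order per man; carry-over that varied with posture or height would reach the distance interactions. The discomfort ratings, taken before and after each condition, are not affected. And the sample size need not rise to 84.

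Severity: minor. The wording is wrong and the correction is cheap before allocation; the carry-over adjustment itself is a trade-off.

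**What to change.** - **Section 5.1.1:** use all six distance orders, seven men each. Give condition sequences 1–7 the orders OFV, FVO, VOF and sequences 8–14 the orders VFO, OVF, FOV, one man per sequence–order pair (14 × 3 = 42).
- **Filling the list:** recruit in blocks of all 14 sequences and rotate the distance orders within each block, so that a stop near 21 stays as close to balanced as possible. This matters: with 21 men and a single distance order per block of seven, the unadjusted variance of F − O is 0.0245, against 0.0136 when balanced.
- **Section 8:** add distance period (first, second, third) to the distance analysis, and prespecify first-order distance carry-over as a sensitivity analysis. It should not be compulsory in the main model, given the break-even of about 0.12 within-man SDs. Six orders make that adjustment affordable; they do not replace it.
- **If Attachment 8 already lists six orders:** correct the sentence in 5.1.1 and make the section 8 additions.
- **If three orders are kept:** call them a Latin square balanced for position only, drop the double-Williams description in 5.5, and state that carry-over between distances is assumed negligible.

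Cost: a new allocation list before the first participant, some wording, one model term and one sensitivity analysis; no extra men or visits. In exchange, condition sequences are no longer fully crossed with every distance order, and the direction of the distance order is tied to the condition square. Exact balance of distance orders at 21 is also lost, since three orders would give seven men each there.
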